Endoscopy with biopsies (histology, IHC, RNA, EndoFLIP) ²		X ^{2, 2a, 4}									X ^{2, 2b}

Study Procedure	Screening Period		24-Week Double-Blind Treatment Period ¹⁸								
	Screening ¹ V1	Screening Endoscopy/ Biopsy ² V2	Baseline V3	V4	V5	V6	V7	V8	V9	V10	DB EOT V11 ³
Week (W)				W1	W2	W4	W8	W12	W16	W20	W24 ³
Day (D)	D-85 to D-29 ¹	D-21 ²	D1	D8	D15	D29	D57	D85	D113	D141	D169
Visit Window (Days [d])		±7 d		±3 d	±3 d	±3 d	±3 d	±3 d	±3 d	±3 d	+7 d
Safety: ^{7, 7a, 18}											
Vital signs ¹³	X	X	X ¹³	X ^{13, 13a}	X ^{13, 13a}	X ^{13, 13a}	X ^{13a}	X ^{13a}	X ^{13a}	X ^{13a}	X
Physical examination	X										X
ECG	X										X
Height	X										X ¹⁴
Weight	X	X	X		X	X	X	X	X	X	X
Adverse events	X	X	X	x	X	X	X	X	X	X	X
Laboratory Testing: ^{7, 7a}											
Hematology, Chemistry	X		X					X			X
Serology tests ¹⁵	X										
Serum FSH	X										
Pregnancy test ¹⁶	Serum	Urine	Urine			Urine	Urine	Urine	Urine	Urine	Urine
Urinalysis	X		X					X			X
PK and ADA: ^{7, 7a}											
PK sample			X					X			X
ADA sample			X					X			X
Biomarkers and Genomics: ^{7, 7a}											
Whole blood DNA (optional)			X								
Whole blood RNA (optional)	X		X								X
Plasma Eotaxin-3	X		X			X		X			X
Serum TARC	X		X			X					X
Serum Total IgE	X		X			X		X			X
Allergen-specific IgE, IgG4	X		X			X		X			X
Future Biomarker Serum/Plasma	X		X			X		X			X

ADA = anti-drug antibody; DB EOT = end of double-blind treatment period; DSQ = Dysphagia Symptom Questionnaire; ECG = electrocardiogram; EoE-EREFS = Eosinophilic Esophagitis-Endoscopic Reference Score; EQ-5D-3L = European Quality of Life 5-dimension (version 3L; 3-level); IHC = immunohistochemistry; PGIC = Patient Global Impression of Change of Dysphagia; PGIS = Patient Global Impression of Severity of Dysphagia; POEM =

Patient-Oriented Eczema Measure; PRO = patient-reported outcome; PK = pharmacokinetic; RQLQ(S)+12 = Rhinoconjunctivitis Quality of Life Questionnaire for patients aged 12+ years; TNSS = Total Nasal Symptom Score; V = visit

Table 2: Part C Schedule of Events – Extended Active Treatment Period

	28-Week Extended Active Treatment Period ¹⁴								
Study Procedure	V11 ¹	V12	V13	V14	V15	V16	V17	V18	EOT V19
Week (W)	W24 ¹	W26	W28	W32	W36	W40	W44	W48	W52
Day (D)	D169	D183	D197	D225	D253	D281	D309	D337	D365
Visit Window (Days [d])	+7 d	±7 d	±7 d	±7 d	±7 d	±7 d	±7 d	±7 d	+7 d
Treatment:²									
Administer study drug ^{3, 4, 4a}	X	X	X	X	X	X	X	X	
Study drug dispensation ^{4, 4a}	X	X	X	X	X	X	X	X	

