Study drug accountability		X	X	X	X	X	X	X	X
Concomitant medications/procedures		X	X	X	X	X	X	X	X
Efficacy:²									
DSQ eDiary ⁵	←----- completed daily by patient -----→								
PGIC ⁶					X				X
PGIS ⁶					X				X
EoE Impact Questionnaire ⁷					X				X
EoE Symptom Questionnaire ⁷					X				X
TNSS ⁸					X				X
RQLQ(S)+12 ⁸					X				X
POEM ⁸					X				X
ACQ-5 ⁸					X				X
EoE-EREFS ^{9, 10}									X ^{10, 10a}
Endoscopy with biopsies (histology, IHC, RNA, EndoFLIP) ¹⁰									X ^{10, 10a}
Safety: ^{2, 2a, 14}									
Vital signs ¹¹	X ¹¹	X ¹¹	X	X	X	X	X	X	X
Height ¹²									X
Weight		X	X	X	X				X
Physical examination									X
ECG									X
Adverse events		X	X	X	X	X	X	X	X

	28-Week Extended Active Treatment Period ¹⁴								
Study Procedure	V11 ¹	V12	V13	V14	V15	V16	V17	V18	EOT V19
Week (W)	W24 ¹	W26	W28	W32	W36	W40	W44	W48	W52
Day (D)	D169	D183	D197	D225	D253	D281	D309	D337	D365
Visit Window (Days [d])	+7 d	±7 d	±7 d	±7 d	±7 d	±7 d	±7 d	±7 d	+7 d
Laboratory Testing: ^{2, 2a}									
Hematology, Chemistry					X				X
Pregnancy test ¹³		Urine		Urine	Urine	Urine	Urine	Urine	Urine
Urinalysis					X				X
PK and ADA: ^{2, 2a}									
PK Sample				X					X
ADA sample				X					X
Biomarkers: ^{2, 2a}									
Whole blood RNA (optional)									X
Plasma Eotaxin-3		X		X					X
Serum TARC									X
Serum Total IgE		X		X					X
Allergen-specific IgE, IgG4		X		X					X
Future Biomarker Serum/Plasma		X		X					X

ADA = anti-drug antibody; DSQ = Dysphagia Symptom Questionnaire; ECG = electrocardiogram; EoE-EREFS = Eosinophilic Esophagitis-Endoscopic Reference Score; EOT = end of extended active treatment period; IHC = immunohistochemistry; POEM = Patient-Oriented Eczema Measure; PRO = patient reported outcome; PGA = physician global assessment; PGIC = Patient Global Impression of Change of Dysphagia; PGIS = Patient Global Impression of Severity of Dysphagia; PK = pharmacokinetic; RQLQ(S)+12 = Rhinoconjunctivitis Quality of Life Questionnaire for patients aged 12+ years; TNSS = Total Nasal Symptom Score; V = visit

Table 3: Follow-up Period, Early Termination Visit, and Unscheduled Visit

Study Procedure	12-Week Follow-Up EOS Visit	Early Termination during 12-Week Follow-Up ¹	Early Termination during Parts A, B, or C ¹	Unscheduled Visit before Rescue Treatment	Unscheduled Visit for Other Reasons
Week (W)	12 weeks after EOT visit				
Day (D)	84 days after EOT visit				
Visit Window (Days [d])	±7 d				
Concomitant medications/procedures ¹⁰	X	X	X	X	X
Efficacy:					

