13. At visits 3 through 6, vital signs (body temperature, blood pressure, respiratory rate, heart rate) should be taken predose and 30 minutes (± 10 minutes) post-dose. Vital signs should be taken predose at all other indicated visits.
 - a. If study drug administration is not possible in-clinic due to staff or patient availability due to COVID-19 restrictions, vital signs pre- and post-dose may not be performed.
14. For adolescent patients only.
15. Includes HIV Ab, HBsAg, HBsAb, HBcAb, HCV Ab, and TB. Tuberculosis testing will be performed on a country-by-country basis according to local guidelines if required by regulatory authorities or ECs.
16. Not required if post-menopausal status confirmed at screening. A negative result must be obtained prior to the randomization visit. In case of a positive urine test, the study treatment will be withheld and a serum pregnancy test to confirm the pregnancy should be performed as soon as possible. A confirmed pregnancy will lead to study drug discontinuation in all cases.
17. The EQ-5D-3L should be administered one time at either visit 1 or visit 3 for newly screened patients.
18. If COVID-19 restrictions limit the availability of staff or the patient to have in-clinic visits, the clinic staff should make every effort to contact the patient at the timepoint of the expected in-clinic visit to collect any AEs (including ISRs), any change in concomitant medications and/or procedures, and monthly pregnancy test results, if required.

8.1.1.2. Footnotes for Table 2

1. This visit is the same as the week 24 visit for Parts A and B (Table 1), and all other assessments indicated for week 24 of Parts A and B (Table 1) should be performed. All pre-dosing procedures (including endoscopy with biopsy) at visit 11/week 24 must be completed prior to administration of study drug for Part C extended active treatment.
2. Study assessments will be performed and blood samples will be collected prior to administration of study drug.
 - a. If COVID-19 restrictions limit the availability of staff or the patient to have in-clinic visits, procedures/sample collection should occur at the next available in-clinic visit. Pregnancy testing must be performed as indicated (in-clinic or at-home) monthly (at a minimum) and results reported in a timely manner.

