3. Patients will be closely monitored at the study site at visits 11 (at a minimum) and 12, if possible, for a minimum of 30 minutes after the administration of study drug. In addition to predose assessments, AEs and vital signs (body temperature, blood pressure, respiratory rate, and heart rate) will be assessed at 30 minutes (± 10 minutes) post-dose.
4. All pre-dosing procedures (including endoscopy with biopsy) at the scheduled visit 11/week 24 must occur prior to dosing with Part C / extended active treatment study drug. On scheduled in-clinic study visit days, study drug will be administered in the clinic (by the patient, site staff, or caregiver). Study drug will be provided for those scheduled doses to be administered at home before the next in-clinic visit. Doses of study drug administered at home should be administered 1 week after the prior dose of study drug. Study drug administration that occurs in clinic should occur per the Schedule of Events in [Table 1](#) and [Table 2](#).
 - a. If COVID-19 restrictions limit the availability of staff or the patient to have in-clinic visits, after visit 11/week 24 patients/caregivers may be dispensed study drug for at-home dosing. Additionally, if the visit 19/ week 52 endoscopy with biopsies is delayed due to COVID-19 restrictions, extended dosing of study drug is allowed until this visit can occur. If extended dosing of the study drug occurs beyond week 51, the clinic staff must contact the patient every 4 weeks (at a minimum) to collect any AEs (including ISRs any change in concomitant medications and/or procedures, and monthly pregnancy test results, if required).
5. DSQ eDiary will be completed once daily by the patients after their last meal of the day but before they go to bed. Site personnel should conduct regular checks of patient eDiary compliance.
6. PGIC and PGIS will be completed by the patient via electronic questionnaire at the indicated site visits. See [Section 8.2.2.5](#) and [Section 8.2.2.6](#).
7. EoE Impact Questionnaire and EoE Symptom Questionnaire will be completed by the patient via electronic questionnaire at the indicated site visits. See [Section 8.2.2.3](#) and [Section 8.2.2.4](#).

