8. TNSS and RQLQ(S)+12 will be administered only to patients with a documented history of allergic rhinitis; ACQ-5 will be administered only to patients with a documented history of asthma, and POEM will be administered only to patients with a documented history of AD. TNSS, POEM, ACQ-5 and RQLQ(S)+12 will be completed via electronic questionnaire and at the indicated site visits. The questionnaires will be administered only to the subset of patients who fluently speak the language in which the questionnaire is presented (based on the availability of validated translations in participating countries). See [Section 8.2.2.7](#), [Section 8.2.2.8](#), [Section 8.2.2.9](#), and [Section 8.2.2.10](#).
9. EoE-EREFS should be completed by the investigator before biopsies for all patients are performed. For Part B enrolled patients, EoE-EREFS will be performed by both the investigators who perform the endoscopies as well as a centralized reading center who will provide EoE-EREFS analysis and scoring from endoscopy imaging. For all endoscopies, the investigators will assess minor esophageal features including mucosal inflammatory and remodeling features.

10. Endoscopy/EoE-EREFS/biopsy procedures should be performed after all other efficacy and safety assessments. The EndoFLIP procedure to measure esophageal distensibility may be performed during the esophagogastroscope procedures at selected North American sites in approximately 150 adult patients.

Note: All randomized patients found to have stomach and/or duodenal abnormalities at baseline will have follow-up stomach and/or duodenal biopsies at weeks 24 and 52.

a. For patients who receive rescue treatment, endoscopy/EoE-EREFS/biopsy procedures will be performed prior to initiation of rescue treatment. Patients undergoing endoscopy/biopsy prior to rescue will not undergo the scheduled endoscopy/biopsy at weeks 24 and 52.

11. At visits 11 and 12, vital signs (body temperature, blood pressure, respiratory rate, heart rate) should be taken predose and 30 minutes (± 10 minutes) post-dose. Only predose vital signs are required at subsequent visits.

12. For adolescents only

13. In case of a positive urine pregnancy test, the study treatment will be withheld and a serum pregnancy test to confirm the pregnancy should be performed as soon as possible. A confirmed pregnancy will lead to study drug discontinuation in all cases.

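### Part C schedules no pregnancy test at V13/week 28, leaving a nominal 42-day gap between tests (weeks 26 to 32) while patients are being dosed

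*Protocol*

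**What the plan says.** Protocol Section 8.1, Table 1 schedules pregnancy tests on treatment at day 1 and at weeks 4, 8, 12, 16, 20 and 24. Table 2 (Part C) schedules urine tests at V12 (week 26), V14 (week 32), V15, V16, V17, V18 and V19 (week 52). Two cells in its row are blank:

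- **V11 (week 24).** This is explained. Footnote 1 to Table 2 (Section 8.1.1.2) makes V11 the same visit as week 24 of Parts A and B and brings in "all other assessments indicated for week 24 of Parts A and B", which includes the week 24 test.
- **V13 (week 28).** Nothing explains this one.

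SAP Section 11.2, Table 7 shows the same row.

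V13 is otherwise a full treatment visit. It is marked for study drug administration and in the row "Study drug dispensation". Footnote 4 adds: "Study drug will be provided for those scheduled doses to be administered at home before the next in-clinic visit".

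The only minimum frequency near the table is in footnote 2a, which opens "If COVID-19 restrictions limit the availability of staff or the patient to have in-clinic visits" and then says "Pregnancy testing must be performed as indicated (in-clinic or at-home) monthly (at a minimum) and results reported in a timely manner". Footnote 13 gives the consequence of a positive result: "A confirmed pregnancy will lead to study drug discontinuation in all cases".

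**The concern.** Because a confirmed pregnancy stops study drug in every case, the time between tests sets how long dosing can continue before a pregnancy is found. The rest of the schedule tests at least every four weeks on treatment. In Table 1 the early one- and two-week visits have no test and the four-week visit does. Part C reverses this: the two-week visit is tested and the four-week visit is not.

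V13 is the only one of the eight Part C dosing and dispensing visits (V11 to V18) without a test. A patient attends, is injected, receives her next three home doses and is not tested. Everyone in Part C receives dupilumab, and patients who had placebo in Part A or B have only just started it. A pregnancy missed at week 26 is next looked for six injections later, although a clinic visit takes place in between.

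**Working it through.** **Inputs.** Test visits and nominal days come from Protocol Section 8.1, Tables 1 and 2. Visit windows: ±3 days for weeks 1 to 20, +7 days at weeks 24 and 52, and ±7 days at V12 to V18. Dosing is weekly, with placebo alternating in the Q2W group (Section 7.1). Assessments precede dosing (footnote 2 to Table 2).

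**Intervals.** The nominal interval is the difference between the study days of consecutive tests. The window range lets each visit fall at either end of its own window.

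| Interval | Nominal days | With windows |
|---|---|---|
| Day 1 to week 4 | 29 − 1 = 28 | 25 to 31 |
| Each 4-week step, weeks 4 to 20 | 28 | 22 to 34 |
| Week 20 to 24 | 169 − 141 = 28 | 28 − 3 = 25 to 28 + 3 + 7 = 38 |
| Week 24 to 26 | 183 − 169 = 14 | at most 14 + 7 = 21 |
| **Week 26 to 32** | **225 − 183 = 42** | **42 − 14 = 28 to 42 + 14 = 56** |
| Each 4-week step, weeks 32 to 48 | 28 | 14 to 42 |
| Week 48 to 52 | 365 − 337 = 28 | 28 − 7 = 21 to 28 + 7 + 7 = 42 |

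Only weeks 26 to 32 exceed 28 days nominally. The nominal length of that interval equals the worst case that windows produce anywhere else on treatment.

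**Injections in the gap.** Testing is pre-dose, so the injections between the week 26 and week 32 tests are those at weeks 26, 27, 28, 29, 30 and 31, which is 6. In the QW group all 6 are active. In the Q2W group 3 are active, whichever of dupilumab or placebo comes first.

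**With a test added at V13 (day 197).** The interval splits into 197 − 183 = 14 days and 225 − 197 = 28 days. With windows, weeks 28 to 32 run from 14 to 42 days. The injections split into 2 (weeks 26, 27) and 4 (weeks 28 to 31), so the longest run falls from 6 to 4. In the Q2W group it falls from 3 active to 2.

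**With the week 26 test moved to V13.** Weeks 24 to 28 are 197 − 169 = 28 days, and every later nominal interval is also 28.

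**The case against.** The strongest reply is that no stated rule is broken. Footnote 2a is conditional on COVID-19 restrictions, and its wording refers back to the schedule, so no text sets a four-week ceiling for patients seen in clinic. That is right, and it is why this is a design point and not a contradiction. If instead the sentence were read as general, the table would fall short of it at week 28, and the same cell would need filling.

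A second reply is that no test has been dropped. Part C has seven tests, as would a strict four-weekly series from week 28 to week 52; the first is simply taken two weeks earlier, soon after placebo patients start dupilumab. The early test is useful, but the protocol does not give this reason, and keeping it does not require leaving week 28 empty.

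Third, the protocol accepts longer gaps elsewhere: the end-of-study test comes 84 days after the end-of-treatment visit (Table 3), within the 12 weeks for which contraception is still required. That period is off drug, so a test then could not prevent further dosing.

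Fourth, the practical effect is small. Exclusion criteria 32 and 33 bar pregnancy and require highly effective contraception. The Introduction puts males at three to four times the frequency of females. Patients may report a pregnancy themselves, and the Risks section (3.2.3.2) describes no embryo-fetal signal. All of this stands and limits the number affected. It does not explain why a dosing visit goes untested.

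**Conclusion.** The concern holds. Weeks 26 to 32 of Part C are nominally 42 days without a pregnancy test (28 to 56 with windows), against 28 days or less for every other on-treatment interval, and six weekly injections fall inside the gap. The statement that it is the only interval above four weeks is true on nominal days; windows can stretch others to 38 days in Parts A and B and 42 in Part C.

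The conclusion assumes that the week 24 test carries into Part C through footnote 1 and that footnote 2a applies only under COVID-19 restrictions. This is a gap in safety scheduling that would touch few patients. It does not bear on any endpoint or on the validity of the trial, but it should be closed because doing so is simple.

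**What to change.** Enter a urine test in the V13/week 28 cell of the pregnancy-test row in Protocol Table 2, and make SAP Table 7 match. Keeping the week 26 test is preferable: the intervals from week 24 are then 14, 14 and 28 days, and no nominal on-treatment interval exceeds 28. The alternative is to move the week 26 test to week 28. That adds no test and gives 28 days throughout, but it gives up the check two weeks after Part C starts.

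The cost is at most one extra urine test per patient of childbearing potential, at a visit where she is already dosed and supplied. There is no extra visit and no effect on endpoints or analyses. The change does need an IRB/EC-approved amendment (Protocol Section 15), so it could reasonably be included in the next one.

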8.1.2. Early Termination Visit

Patients who are withdrawn from the study will be asked to return to the clinic for an ET visit consisting of the assessments described in [Table 3](#).

8.1.3. Unscheduled Visits before Rescue Treatment

Before patients receive rescue treatment, efficacy assessments, PK and ADA sampling specified in [Table 3](#) should be performed.

8.1.4. Unscheduled Visits for Other Reasons

All attempts should be made to keep patients on the study schedule. Unscheduled visits may be necessary to repeat testing following abnormal laboratory results, for follow-up of AEs, or for any other reason, as warranted.

8.2. Study Procedures

8.2.1. Procedures Performed Only at the Screening/Baseline Visit

The following procedures will be performed for the sole purpose of determining study eligibility or characterizing the baseline population: serum follicle stimulating hormone (FSH) (for confirmation of menopausal status) and serology tests (HIV Ab, HBsAg, HBcAb, HCV Ab, and TB). Tuberculosis testing will be performed on a country-by-country basis according to local guidelines if required by regulatory authorities or ECs.

8.2.2. Efficacy Procedures

8.2.2.1. Endoscopy with EoE-EREFS and Biopsies, and Photographs

During the endoscopy procedure, EoE-EREFS and biopsies will be performed in the listed order. Training will be provided to study sites on performing this procedure. All biopsies performed during this study will be evaluated by a qualified central histology laboratory. Photographs and/or video may be taken as part of the endoscopic procedure and biopsy collection. For Part B enrolled patients, video imaging should be collected for EoE-EREFS analysis and scoring by a centralized reading center.

The endoscopy/EoE-EREFS/biopsy procedure will be performed per the Schedule of Events in [Table 1](#), [Table 2](#), and [Table 3](#).

EoE-EREFS

The EoE esophageal characteristics will be analyzed based on the EoE-EREFS, a validated scoring system for inflammatory and remodeling features of disease using both overall scores and scores for each individual characteristic ([Hirano, 2013](#)). The proximal and distal esophageal regions will be scored separately; the score for each region ranges from 0 to 9 and the overall score ranges from 0 to 18. The major esophageal features include:

- Edema (absent, present)
- Rings (absent, mild, moderate, severe)
- Exudates (absent, mild, severe)
- Furrows (absent, mild, severe)
- Stricture (absent, present)

EoE-EREFS should be completed by the investigator before biopsies for all patients are performed. For Part B enrolled patients, EoE-EREFS will be performed by both the investigators who perform the endoscopies as well as a centralized reading center who will provide EoE-EREFS analysis and scoring from endoscopy imaging. The centralized reading will be used for analysis, if available. If the centralized reading is not available, the EoE-EREFS performed by the investigator will be used for analysis. A copy of the EoE-EREFS is provided in the study regulatory binders.

In addition to the major features above, data for the following minor features will also be captured by the physician performing the endoscopy procedure:

- Crepe paper esophagus (mucosal fragility or laceration upon passage of diagnostic endoscope): absent, present
- Narrow caliber esophagus (reduced luminal diameter of the majority of the tubular esophagus): absent, present
- Stricture diameter

Mucosal changes associated with gastroesophageal reflux disease will also be recorded using the Los Angeles classification system for erosions (No Erosions or Grade A, B, C, or D).

Biopsies

Biopsies will be obtained by endoscopy at the second screening visit (visit 2, day -21 ± 7), week 24 and week 52 visits, and immediately prior to start of rescue medication or procedures during the double-blind treatment period. The screening endoscopy should be performed at a time during the screening period that will allow results to be available prior to day -1 for assessment of eligibility. A total of 9 mucosal pinch biopsies will be collected at each time point from 3 esophageal regions: 3 proximal, 3 mid, and 3 distal. Two samples from each region will be used for the histology (needed for study inclusion criteria, as well as endpoint assessment) and other tissue analyses (may include but not limited, to immunohistochemistry [IHC], RNA scope (in situ hybridization), and RNA sequencing). To participate in the study, patients must have a peak intraepithelial eosinophil count ≥ 15 eos/hpf (400 \times) in at least 2 of the 3 esophageal regions sampled. Any remaining tissue blocks will be banked for exploratory research. The third sample from each region will be processed for RNA analyses.

In addition, biopsy specimens from the stomach and/or duodenum will be obtained at visit 2 in all patients <18 years of age to rule out alternate etiologies of esophageal eosinophilia. Targeted, stomach and/or duodenal biopsies will be obtained in adults only in the event of abnormal endoscopic findings (other than typical EoE findings) or clinical suspicion of alternate etiologies. Gastric biopsy samples should include 2 samples from the antrum and 2 samples from the body. Duodenal biopsy samples should include 2 bulb samples and 2 from another portion of the duodenum. All randomized patients found to have stomach and/or duodenal abnormalities at baseline will have follow-up stomach and/or duodenal biopsies at week 24 and week 52.

Biopsy samples will be sent to a central pathology laboratory for processing and analysis. If required by the investigator institution, biopsy samples will be processed and analyzed by the local laboratory, and the processed specimen will be sent to the central pathology laboratory for central reading. These samples will be assessed for peak eos per hpf and EoE Grade Scores and Stage Scores will be assigned. EoE Grade and Stage Scores evaluate eight features: eosinophil density, basal zone hyperplasia, eosinophil abscesses, eosinophil surface layering, dilated intercellular spaces, surface epithelial alteration, dyskeratotic epithelial cells, and lamina propria fibrosis (absent/present). Additional analyses on these data may also be performed.

Assessment of lamina propria fibrosis may not be possible if the esophageal biopsy specimens do not contain adequate amounts of subepithelium lamina propria and then will not be included in the overall EoE Grade and Stage Scores. Severity (grade) and extent (stage) of abnormalities will be

scored using a 4-point scale (0 normal; 3 maximum change). The endoscopy with biopsies procedure will be performed the same way at all scheduled visits.

Histology results will be interpreted by a pathologist at a central pathology reading center who will be blinded to the treatment assignment. Detailed instructions for biopsy sample collection and handling will be provided in the study regulatory binders.

EndoFLIP

A substudy of esophageal distensibility utilizing the endolumenal functional lumen imaging probe (EndoFLIP, Medtronic, USA) may also be performed at selected North American sites in approximately 150 adult patients, with measurements taken as part of the esophagogastroscopy procedure performed at screening, week 24 and week 52. The EndoFLIP procedure must be performed before biopsies are collected. Procedural order should be: EREFS/imaging, EndoFLIP, then biopsies. The EndoFLIP device is a catheter-based procedure that measures the cross-sectional area at multiple sites along the esophagus with simultaneous intraluminal pressure recordings during volumetric distension of the esophagus. The analyses of cross sectional area versus pressure relationships of the esophagus allow for determination of esophageal compliance as well as the distensibility plateau. The distensibility plateau has been shown to be significantly reduced in adult patients with EoE compared to healthy controls (Kwiatek, 2011). Moreover, the esophageal distensibility has been associated with outcomes of both food impaction and need for esophageal dilation (Nicodème, 2013). Details of the EndoFLIP procedure will be provided in the study regulatory binders.

Photographs and/or Video

Photographs and/or video may be taken by the site as part of the endoscopic procedure and biopsy collection. A copy of these photographs and/or video will be requested from the study sites. Details for collecting and sending these photographs and/or video will be provided in the study regulatory binders. For Part B enrolled patients, video imaging should be collected for EoE-EREFS analysis and scoring by a centralized reading center.

